1.2.4. Efficacy, Immunogenicity, and Safety Parameters

1.2.4.1. Efficacy Parameters

Efficacy will be measured through the following study parameters.

- Change in the number of RRP surgical interventions in the year following Day 0, compared to the year prior.
- Change in RRP Staging Assessment Score (see Section 1.2.4.1.1.)

■ [REDACTED]

- miRNA profile as related to the reduction in frequency of surgical intervention.

1.2.4.2. Immunogenicity Parameters

The immunogenicity parameters for this study include measurement of [REDACTED] cell mediated immune responses in blood samples taken at baseline and periodic intervals:

- Secondary Parameters
 - Antigen-specific cellular immune responses assessed by:
 - IFN- γ secreting cells in peripheral blood mononuclear cells (PBMCs) by ELISpot
 - T cell phenotype and lytic potential in PBMCs by flow cytometry

■ [REDACTED]

- Assessment of pro-inflammatory and immunosuppressive elements in resected tumor tissue, if available.

■ [REDACTED]

■ [REDACTED]

■ [REDACTED]

■ [REDACTED]

■ [REDACTED]

■ [REDACTED]

■ [REDACTED]

■ [REDACTED]

1.2.4.3. Safety Parameters

Safety evaluations performed during the study include physical examinations, measurement of vital signs, injection site reactions, pain, and concomitant medications/procedures. Safety and tolerability of INO-3107 will be assessed by reported AEs and SAEs as measured and graded by the CTCAE v. 4.0.

Treatment-emergent adverse events (TEAEs) are collected throughout study. All TEAEs that occur within 7 days following each injection will be summarized separately. All adverse events including SAEs, unexpected adverse device effects (UADEs) that relate to the rights, safety, or welfare of subjects, and DLTs, as well as clinically significant changes in laboratory parameters and vital signs from baseline assessments will be assessed.

2. SUBJECT POPULATION

2.1. Population Definitions

The following populations provide the basis for analysis and presentation of data:

- The intention to treat (ITT) population includes all subjects who are eligible.
- The modified intention to treat (mITT) population includes all subjects who receive at least one dose of INO-3107.
- The per-protocol population includes subjects who receive all doses of INO-3107 and have no protocol violations. (Subjects excluded from the PP population based on protocol deviations discovered after or during treatment, will be identified and documented prior to locking of the trial database and excluded from the PP population.)
- The safety population includes all subjects who receive at least one dose of INO-3107.

2.2. Protocol Deviations

At the discretion of the Sponsor, certain protocol deviations, as determined by sponsor review of the data prior to locking of the study database and the conduct of statistical analyses, will result in the removal of a subject's data from the PP population.

The Sponsor or designee will be responsible for producing the final protocol deviation file (formatted as a Microsoft Excel file), in collaboration with Veristat and the data monitoring group as applicable; this file will include a description of the protocol deviation which warrants exclusion from the PP population. This file will be finalized prior to hard database lock.

All protocol deviations will be presented in a data listing.

3. GENERAL STATISTICAL METHODS

3.1. Sample Size Justification

Formal power calculation was not performed for this study, as the primary statistics are descriptive. For the safety endpoints, among n=30, we hypothesize that the true serious adverse event incidence is <12%, if no additional SAEs are observed.

3.2. General Methods

All data listings that contain an evaluation date will contain a relative study day (Rel Day). Pre-treatment and on-treatment study days are numbered relative to the day of the first dose of study medication (Day 0) which is designated as Rel Day 1. The preceding day is Rel Day -1, the day before that is Rel Day -2, etc. There is no Rel Day 0.

All output will be incorporated into Microsoft Word (.rtf) files, or Adobe Acrobat PDF files, sorted and labeled according to the International Conference on Harmonisation (ICH) recommendations, and formatted to the appropriate page size(s).

Tabulations will be produced for appropriate demographic, baseline, efficacy, immunogenicity, and safety parameters. For categorical variables, summary tabulations of the number and percentage of subjects within each category (with a category for missing data) of the parameter will be presented. For continuous variables, the number of subjects, mean, median, standard deviation (SD), minimum, and maximum values will be presented. Summarizations will be presented for all subjects in the specified population as described in the next section of this SAP. These summary statistics will be presented with 2-sided confidence intervals (CI) on selected parameters, as described in the sections below.

3.3. Computing Environment

All statistical analyses will be performed using SAS statistical software Version 9.4, unless otherwise noted. Medical history and adverse events will be coded using the Medical Dictionary for Regulatory Activities (MedDRA) Version 23.0 or higher. Concomitant medications will be coded using the B3 World Health Organization (WHO) Drug Global Dictionary, March 2020.

3.4. Baseline Definition

For all analyses, baseline will be defined as the most recent measurement prior to the first administration of study drug.

3.5. Methods of Pooling Data

Data will be pooled across study sites .

3.6. Adjustments for Covariates

No formal statistical analyses that adjust for possible covariate effects are planned.

3.7. Multiple Comparisons/Multiplicity

Multiplicity is not of concern for this study with a descriptive interpretation.

3.8. Subpopulations

All safety, efficacy, and immunogenicity data will be analyzed separately and combined for subjects by number of prior surgical interventions (≤ 2 , 3-5, and ≥ 6), [REDACTED] and overall.

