3.4 SECONDARY ENDPOINT(S)

1. Number of RRP surgical interventions in the one year following Day 0, compared to the one year prior to Day 0.
2. Changes in Staging Assessment as measured by the RRP Staging Assessment score over time.
3. Antigen-specific cellular immune responses assessed by:
 - IFN- γ secreting cells in peripheral blood mononuclear cells (PBMCs) by ELISpot
 - T cell phenotype and lytic potential in PBMCs by flow cytometry
4. Assessment of pro-inflammatory and immunosuppressive elements in resected tumor tissue, if available.
5. miRNA profile as related to the reduction in frequency of RRP surgical intervention, if possible.

[REDACTED]

- [REDACTED]
- [REDACTED]
- [REDACTED]
- [REDACTED]
- [REDACTED]
- [REDACTED]
- [REDACTED]
- [REDACTED]

[REDACTED]

- [REDACTED]
- [REDACTED]
- [REDACTED]
- [REDACTED]
- [REDACTED]
- [REDACTED]
- [REDACTED]
- [REDACTED]

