3.7 EFFICACY ASSESSMENT

A detailed medical history will be obtained for each subject which will include documentation of HPV-6 and/or HPV-11 RRP, a list of RRP surgeries and therapies occurring within 3 years prior to screening, and any periods of remission. Subjects must have had at least two surgical RRP interventions (including laser) in the year prior to and including Day 0, to be eligible for the study. Subjects must require RRP intervention at the time of entry into this study and will undergo surgical removal of their papilloma(s) during screening, within 14 days prior to Day 0 dosing, to maximize standardization of baseline staging across subjects.

The efficacy assessment will be based upon the number of RRP surgical interventions in the 52 weeks post Day 0 compared to the number of RRP surgical interventions in

the year prior to Day 0 dosing. RRP surgical interventions include laser therapies. The trial will also evaluate changes in RRP Staging Assessment over time as a secondary endpoint.

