4.0 CLINICAL TRIAL POPULATION

4.1 INCLUSION CRITERIA

1. Provide written IRB-approved informed consent in accordance with institutional guidelines;
2. Be ≥ 18 years of age on the day of signing the informed consent, and able and willing to comply with all trial procedures;
3. Have histologically documented HPV-6- or HPV-11-positive respiratory papilloma or documentation of low-risk positive HPV using a Sponsor approved HPV-6/11 type-specific assay;
4. Have a requirement for frequent RRP intervention in order to remove or resect respiratory papilloma, as defined as at least two RRP surgical (including laser) interventions in the year prior to and including Day 0;
5. Must be appropriate candidate for upcoming surgical intervention per investigator judgement and RRP Staging Assessment score (see [Section 6.4.5](#));
6. Have adequate bone marrow, hepatic, and renal function as defined by: ANC (Absolute Neutrophil Count) ≥ 1000 cells/mm³, platelets $\geq 50,000$ /mm³, hemoglobin ≥ 9 g/dL; concentrations of total serum bilirubin within 1.5 x upper limit of normal (ULN), AST and ALT within 1.5 x ULN, serum creatinine ≤ 1.5 x ULN;
7. Agree that during the trial, male participants will not father a child, and female participants cannot be or become pregnant if they are of child-bearing potential. Subjects must meet one of the below requirements:

- a. Be of non-childbearing potential (≥ 12 months of non-therapy-induced amenorrhea, confirmed by follicle stimulating hormone [FSH], if not on hormone replacement;
- b. Be surgically sterile (vasectomy in males or absence of ovaries and/or uterus in females);
- c. Agree to use one highly effective or combined contraceptive methods that result in a failure rate of $< 1\%$ per year during the treatment period and at least through week 12 after last dose. Periodic abstinence (e.g., calendar, ovulation, symptothermal, or post-ovulation methods) and withdrawal are not acceptable methods of contraception.
- d. Agree to abstinence from penile-vaginal intercourse, when this is the subject's preferred and usual lifestyle.

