8.5.2 Secondary Analyses

8.5.2.1 EFFICACY

The frequency of RRP surgical interventions in the year following the first dose of investigational product, compared to the frequency in the year prior to Day 0 dosing, will be summarized descriptively using mean fold-change and a 95% t-distribution-based CI.

Changes in RRP Staging Assessment scores from baseline pre-dose to each post-dose evaluation will be analyzed. Median changes and associated 95% confidence intervals will be computed.

[REDACTED]

Intersurgical intervals will also be summarized.

Analyses will be summarized and presented by number of prior surgical interventions (≤ 2 , 3-5, and ≥ 6) and overall. Efficacy analysis using the mITT population will be conducted. The PP population will also be used for a supportive analysis.

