4.3.1. Efficacy Analyses

The parameters that follow will be analyzed to support the conclusions of the primary analysis. For categorical endpoints, frequency and percentages will be calculated. For continuous variables, means, medians, or changes in percentage will be summarized. Where appropriate, 95% confidence intervals will be calculated (see specific analysis discussed subsequently). Analyses will be summarized and presented by number of prior surgical interventions (≤ 2 , 3-5, and ≥ 6), [REDACTED] and overall.

.

- Secondary analyses
 - Frequency of RRP surgical interventions in the year following intervention, compared to the frequency in the year prior will be presented as median difference with 95% CI based on non-parametric methodology.
 - Percent reduction in RRP surgical intervention as a categorical variable (categories consist of percent ranges), with frequency and percentages.
 - Change in surgical interval for prior to intervention to post will be presented along with median, mean, and 95% confidence intervals.
 - Change in stage as measured by the RRP Staging Assessment. Median changes and associated 95% confidence intervals will be computed.
 - The relationship of microRNA (miRNA) profiles with frequency of surgical intervention will be described using regression analysis.

■ [REDACTED]

■ [REDACTED]

■ [REDACTED]

In addition to these tabulations, by-subject listings will be provided for all efficacy endpoints.

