5. CHANGES TO PLANNED ANALYSES

- The analysis of frequency of RRP interventions will be based on a median change instead of a mean fold-change due to the nature of the data.
- There will be no formal interim analysis; however, a subset analysis of the first 21 subjects will be conducted

I

[REDACTED]

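### If prior surgeries are counted over the year before Day 0, the efficacy strata share the count that is subtracted in the outcome, so heavier strata show larger falls without any drug effect

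*SAP*

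**What the plan says.** **Strata.** SAP section 3.8 has safety, efficacy and immunogenicity data "analyzed separately and combined for subjects by number of prior surgical interventions", with groups ≤2, 3-5 and ≥6. Protocol section 8.5.2.1 says the same for efficacy: "Analyses will be summarized and presented by number of prior surgical interventions". Neither gives a look-back period.

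**Outcome.** The endpoint in Protocol section 3.4 is "Number of RRP surgical interventions in the one year following Day 0, compared to the one year prior to Day 0". In SAP section 4.3.1 the comparison "will be presented as median difference with 95% CI based on non-parametric methodology". SAP section 5 records the switch from the protocol's measure: the analysis "will be based on a median change instead of a mean fold-change due to the nature of the data". A second display is "Percent reduction in RRP surgical intervention as a categorical variable (categories consist of percent ranges), with frequency and percentages".

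**Baseline count.** Eligibility (Protocol section 4.1) requires "at least two RRP surgical (including laser) interventions in the year prior to and including Day 0". Protocol section 3.7 also has every subject undergo papilloma removal within 14 days before Day 0, and has the medical history record "a list of RRP surgeries and therapies occurring within 3 years prior to screening".

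**Safeguards.** The trial has one arm (Protocol section 8.2). SAP section 3.6 plans no covariate adjustment. The visible text does not mention regression to the mean.

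**The concern.** One year is the only period that fits the eligibility rule, the endpoint and the cut-points together; ≤2 then means exactly two. On that reading the stratifying variable is also the baseline in the difference. Some subjects are in ≥6 because that year was unusually bad, and some are in ≤2 because it was unusually good. Both groups tend to move back towards their usual rate. The possible fall is also capped at two in the lowest group and at six or more in the highest.

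With no control arm, nothing in the table separates this movement from a treatment effect. A reader of the stratum medians could conclude that the product works better in heavier disease. The protocol's summary of changes for version 3.0 says the trial should give an early read on efficacy in support of Phase 3, so the table is likely to be looked at with that in mind.

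**Working it through.** The plan gives no figure for the strata, so there is none to reproduce. The question is what the planned display shows when there is no effect.

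**Inputs from the documents.** Cuts ≤2, 3-5, ≥6. Outcome Y − X, where X is the prior-year count and Y the post-year count. Entry requires X ≥ 2. One surgery falls just before Day 0.

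**Assumptions (not in the documents).** Each subject has a constant annual rate, gamma-distributed with mean m = 3 or 4 and between-subject CV c = 0.3, 0.5 or 0.8. Yearly counts are Poisson given that rate. The screening surgery is either not added to X or added to it. This makes 12 scenarios, all with no treatment effect.

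**Formula.** With a = 1/c² and b = a/m:
- E[Y | X] = (a + X)/(b + 1)
- E[Y − X | X] = (a − bX)/(b + 1)

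The expected change therefore drops by b/(b + 1) per extra prior surgery. For m = 4, c = 0.8: a = 1.5625, b = 0.39, drop 0.28. For m = 3, c = 0.3: a = 11.11, b = 3.70, drop 0.79. It is never zero while counts vary within a subject. With no within-subject variation the gradient is 0.

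**Example: m = 4, c = 0.5, screening surgery not added.** a = 4 and b = 1, so E[Y | X] = (4 + X)/2.

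| Stratum | Mean X | Mean Y | Mean change |
|---|---|---|---|
| ≤2 | 2.00 | 3.00 | +1.00 |
| 3-5 | 3.88 | 3.94 | +0.06 |
| ≥6 | 7.88 | 5.94 | −1.94 |

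**All 12 scenarios (simulation, no effect).**

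| Stratum | Median change | Mean change |
|---|---|---|
| ≤2 | −1 to +1 | −0.3 to +1.5 |
| 3-5 | −1 to 0 | −0.9 to +0.1 |
| ≥6 | −3 to −2 | −3.4 to −1.4 |

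The gap in mean change, ≥6 minus ≤2, is −2.0 to −4.0 surgeries. A second model, with gamma-distributed gaps between surgeries (shape 1 or 3, median gap 90 to 180 days), agrees in direction and extends the ≥6 median to −4.

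**At trial size.** In 5,000 no-effect trials of 30 subjects in each of three scenarios (c = 0.5), the ≥6 median fell further than the ≤2 median in 94-96% of trials where both groups were occupied.

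**Percent reduction.** The no-effect share with a reduction of at least 50%, in the order ≤2, 3-5, ≥6, has no fixed direction:
- 26/31/53% (m = 3, c = 0.3, screening surgery not added)
- 55/42/37% (m = 3, c = 0.8, screening surgery added)
- 43/28/19% (gap model, shape 3, median gap 90 days)

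**A real effect.** Halving every subject's rate in the example gives E[Y | X] = (4 + X)/4 and mean changes of −0.50, −1.91 and −4.91. The gap is −4.91 + 0.50 = −4.41. With no effect it is −1.94 − 1.00 = −2.94.

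**Another window.** With strata cut on a three-year total, the no-effect mean changes are −0.51, −0.28 and −0.39, so there is no gradient towards heavier disease. About 0%, 7% and 93% of subjects would then fall in the three groups, which argues against that reading.

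**Strata on the two earlier years, annualised.** The gap becomes +0.1 to +0.8. In the example, mean changes are −0.69, −0.37 and −0.13; with the screening surgery added they are −1.26, −1.10 and −1.03. Using the cut-points proposed under the fix moves each of these by less than 0.1. A two-year mean of 2.5 or 5.5, which fits none of the current groups, occurs in about 11-17% of subjects.

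**The case against.** **The window is inferred.** A reader might take the plan to say that the strata use the prior-year count. It does not, and on a three-year total the gradient disappears. This stands: what is documented is an undefined window, and the rest is conditional on the one-year reading.

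**Percent reduction.** A reader might expect the same gradient in every efficacy display. The figures above do not support that; the share with at least 50% reduction can favour the lightest stratum.

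**Not all of a gradient is artefact.** A uniform proportional effect also gives larger absolute falls in heavier strata. A reader might infer that any observed gradient is false; that goes too far. The display cannot tell the two apart.

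**Use of the strata.** No text says that they will select a Phase 3 population. Another grouping factor is redacted beside them, so they cannot be called the main subgroup display. No hypothesis is tested, and about 30 subjects are split three ways. This lowers the importance. It does not remove the problem, since the trial-size runs show the pattern in nearly every no-effect trial under the assumptions used.

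**Re-cutting has limits.** The protocol's summary of changes says that the three-year surgery requirement was dropped to admit subjects with a break in treatment, and that older history is taken where available. Years −2 and −3 may therefore be missing or atypical. SAP section 3.12 reports that an analysis of the first 21 subjects has been done, so replacing the strata now would be a change made after data were seen. Both points favour adding a display rather than replacing the planned one.

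**Conclusion.** The point holds conditionally. The window needs stating in any case. If it is the prior year, the planned median difference will fall more in heavier strata with no drug effect: about −1 to +1 in ≤2 against −2 to −4 in ≥6 under the assumed models. The direction for the difference in counts follows from the design. The size rests on assumed rates and within-subject variation, for which the documents give no figure.

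The overall estimate is not altered by how the strata are cut. Its own no-effect decline, about one surgery when the screening surgery is counted, comes from the entry rule and that surgery and is a separate matter. This is a cheap improvement of minor to moderate importance.

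**What to change.** In SAP sections 3.8 and 4.3.1:

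1. State the period over which prior surgical interventions are counted, and whether the screening surgery is included.
2. Keep the prior-year strata, but show the post-year count or rate beside the change in each, so that movement towards the middle is visible.
3. Add one efficacy display with strata cut on the annualised count in years −2 and −3, from the history already collected. Use cut-points that cover half-values, for example <2.5, 2.5 to <5.5 and ≥5.5, and an unknown group for missing history. Record it in SAP section 5 as an addition.
4. State that a gradient in change across prior-year strata is expected without any effect and will not be read as differential benefit.

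The cost is one derived variable, one table and a few sentences. Older history may be incomplete or atypical for some subjects.

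The new strata remove only the gradient of larger falls in heavier disease. Without an effect, every stratum would still show about −1.0 to −1.5 surgeries when the screening surgery is counted. The share with at least 50% reduction would still lean towards the lightest group (39/26/17% in the example without the screening surgery), so those categories need the same caution.

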3.9. Withdrawals, Dropouts, Loss to Follow-up

A subject will be considered to have completed the trial when they have completed all study visits through Week 52. Subjects may withdraw consent at any time for any reason or be dropped from the trial at the discretion of the Investigator should any untoward effect occur. In addition, the Investigator or the Sponsor has the right to discontinue a subject from the trial at any time.

The Investigator must notify the Sponsor within 24 hours when a subject has been discontinued/withdrawn due to an AE. Any AEs and/or SAEs present at the time of discontinuation/withdrawal should be followed in accordance with the safety requirements outlined in the protocol. Subjects who are withdrawn or discontinued from the study will not be replaced.

3.10. Missing, Unused, and Spurious Data

When tabulating AE data, partial dates will be handled as follows in order to determine treatment emergence. If any of the day, month, or year is missing, the onset date will be set to the earliest date that is consistent with any non-missing date information, unless the non-missing date information is the same as study treatment start. In this case, in order to conservatively report the event as treatment-emergent, the onset date will be assumed to be the date of start of treatment. A completely missing onset date will be coded as the day of start of treatment.

A prior medication is defined as any medication that was used and has a stop date before the start of the trial (before Dose #1 on Day 0). A concomitant medication is defined as any medication that has a stop date that is on or after the date of first dose of study drug. For prior and concomitant medications, partial start dates will not be imputed, as stop dates determine prior versus concomitant. Partial stop dates will be assumed to be the latest possible date consistent with the partial date.

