8.5 DESCRIPTION OF STATISTICAL METHODS

8.5.1 Primary Analyses

The primary analyses for this trial are safety analyses of Treatment Emergent Adverse Events (TEAE) and clinically significant changes in safety laboratory parameters from baseline.

TEAEs are defined for this trial as any AEs that occur following Day 0 following administration of study drug (IM + EP), until 30 days following the last dose. All TEAEs will be summarized among the Safety Population by frequency. These frequencies will be presented overall, by system organ class and by preferred term, the percentage of subjects affected. Additional frequencies will be presented with respect to maximum severity and to strongest relationship to study treatment. Multiple occurrences of the same

AE will be counted only once following a worst-case approach with respect to severity and relationship to study treatment. All serious TEAEs will also be summarized as above.

The main summary of safety data will be based on TEAEs. For this summary, the frequency of preferred term events will be calculated along with 95% confidence intervals, using the exact method of Clopper-Pearson. Separate summaries will be based on events occurring within 7 days of any dose and regardless of when they occurred. AEs and SAEs that are not TEAEs or serious TEAEs will be presented in listings.

For AE data, partial start dates will be imputed to the date of treatment to conservatively report the event as treatment-emergent, whenever the portion of the date is consistent with that of the study treatment. Otherwise, it will be imputed to the earliest date consistent with the partial date. A completely missing onset date will be imputed as the day of treatment. Partial stop dates will be assumed to be the latest possible day consistent with the partial date.

AE duration will be calculated as (Stop Date – Start Date) + 1.

Laboratory response variables will be descriptively summarized per time point and as changes from baseline including 95% confidence intervals. Shifts from baseline according to the CTCAE will also be presented. Laboratory values considered clinically significant will be presented in listings.

All of the safety analyses will be conducted on the subjects in the safety analysis set.

Analyses will be summarized and presented by number of prior surgical interventions (≤ 2 , 3-5, and ≥ 6) and overall.

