4.4.2. Adverse Events

All adverse events (AEs) will be coded using the MedDRA coding system (v. 25.0 or higher) and displayed in tables and data listings by SOC and PT. AEs will be summarized for the safety population by number of prior surgeries, [REDACTED] and overall. Tables will describe the incidence of AEs. In these tabulations, each subject will contribute only once (i.e., the most related occurrence or the most intense occurrence) to each of the incidences in the analysis, regardless of the number of episodes. Multiple occurrences of the same AE will be counted only once following a worst-case approach with respect to severity and relationship to study treatment.

Adverse events with onset after the administration of study medication through 30 days following the last dose, are considered treatment emergent adverse events (TEAEs). The frequency and 95% Clopper-Pearson CIs of TEAEs will be calculated. An overall summary of TEAEs will include the number and percentage of subjects with any TEAE, any TEAE assessed by the Investigator as related to treatment, any TEAE by severity grade, any SAE, any pre-treatment AE, any AE leading to discontinuation of treatment, and any AE leading to death and separately for events occurring within 7 days of any dose and regardless of when they occurred. AEs and SAEs that are not TEAEs or serious TEAEs will be presented in listings:

- All TEAEs
- All TEAEs by most recent dose*
- All TEAEs by severity grade
- All TEAE considered treatment-related
- All TEAEs by most recent dose and severity grade *
- All AEs that occur any time within 52 Weeks on Study
- All treatment related TEAEs by most recent dose *

*TEAEs of this type will also be presented within 7 days.

All adverse events occurring on-study will be provided in by-subject data listings along with subject deaths, SAEs, Grade 3/4 level events and DLTs, and AEs leading to withdrawal.

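### SAP 3.10 imputes incomplete AE onset dates to treatment start without checking the stop date, so an event that ended before the first dose can count as a TEAE; no partial-date rule is given for the by-dose and 7-day tables

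*SAP*

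**What the plan says.** SAP 3.10 sets out how incomplete AE dates are completed. It opens by stating the purpose: "partial dates will be handled as follows in order to determine treatment emergence". By default, "the onset date will be set to the earliest date that is consistent with any non-missing date information". The exception is a date whose known parts match treatment start; then, "in order to conservatively report the event as treatment-emergent, the onset date will be assumed to be the date of start of treatment". When nothing is known, "A completely missing onset date will be coded as the day of start of treatment". The AE paragraph does not mention the AE stop date. The stop-date sentence in that section concerns medications.

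Protocol 8.5.1 has a similar rule with a different anchor: "partial start dates will be imputed to the date of treatment to conservatively report the event as treatment-emergent". It also says "Partial stop dates will be assumed to be the latest possible day consistent with the partial date" and "AE duration will be calculated as (Stop Date – Start Date) + 1". It does not make the onset and stop rules constrain each other.

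The trial gives four doses (Day 0, Weeks 3, 6 and 9; protocol 5.2). SAP 4.4.2 plans "All TEAEs by most recent dose", with versions by severity and by relatedness, and repeats these for events within 7 days.

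**The concern.** There are two separate problems.

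**Impossible records.** AEs are collected from informed consent (protocol 7.9), screening can last 60 days (6.1.1), and papilloma surgery takes place 0-14 days before Day 0. The database will therefore hold pre-dose events. Treating an uncertain event as treatment-emergent is a reasonable conservative choice. It stops being reasonable when the recorded stop date shows that the event was over before any dose. TEAEs are the primary analysis, so such records would add false events to it.

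**A gap for the dose-level tables.** The rule is written to decide treatment emergence relative to the first dose. The by-dose and 7-day tables ask a different question, namely which dose the event followed and how soon. The SAP does not say how a partial date enters them. If the programmer reuses the imputed date, events after later doses shift towards earlier ones, and some drop out of the 7-day tables. For those tables the rule would not be conservative.

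**Working it through.** The documents state no figure for this rule, so there is none to reproduce. The check applies SAP 3.10 as written.

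**Inputs from the documents:** the SAP 3.10 onset rule; doses at Days 0, 21, 42 and 63 (nominal); surgery 0-14 days and screening up to 60 days before Day 0; the duration formula in protocol 8.5.1.

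**Assumptions:** Day 0 falls on each of the 365 dates of 2021 with equal weight; onsets are uniform over the stated range; the day of onset is missing and the stop date is known. For pre-dose events, durations of 1, 2, 3 and 7 days are averaged.

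**1. A single record.** Day 0 is 20 March, surgery was on 10 March, and a sore throat has onset in March (day unknown) and stop 14 March. The month matches, so onset becomes 20 March and the event is a TEAE. Duration = 14 - 20 + 1 = -5 days. In general a stop on Day 0 minus 1 gives -1 + 1 = 0, and any earlier stop gives a negative value. Only the treatment-start anchor can do this; the earliest consistent date cannot fall after the true stop.

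**2. How often pre-dose events convert.** An event *b* days before Day 0 is anchored to Day 0 if both fall in the same month. Over 365 dates and 12 months (*b* up to 28) that share is 1 - 12*b*/365. For *b* = 1 to 14 the mean is 7.5, giving 1 - 90/365 = 75.3%.

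| Known part of onset | 1-14 days pre-dose | 1-60 days pre-dose |
|---|---|---|
| Month and year | 75.3% | 24.5% |
| Year only | 97.9% | 91.6% |
| Nothing | 100% | 100% |

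**3. With a stop-date bound** (day missing), the first row falls to 14.6% and 3.4%. The remainder are events still ongoing on Day 0, which the conservative rule is meant to catch. The bound removes 75.3 - 14.6 = 60.7 and 24.5 - 3.4 = 21.1 percentage points.

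**4. By-dose tables, if the imputed date is reused.** Take an onset *e* days after dose 2, 3 or 4, with the day missing. The right dose survives only if the 1st of the onset month falls on or after the dose date, that is, if the onset's day of month is at most *e* + 1. That share is 12(*e* + 1)/365. For *e* = 0 to 6 the mean of *e* + 1 is 4, giving 48/365 = 13.2%, so 86.8% go to an earlier dose. With only the year known it is 98.9%, and with nothing known 100%. A stop-date bound leaves the 86.8% unchanged, because the anchor causes this shift.

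**5. 7-day tables, same condition.** Counting days 0-7 after a dose as within 7 days, 42.7% (dose 2) and 60.5% (doses 3 and 4) fall outside every window, a mean of about 55%. Counting days 0-6, the figures are 46.0% and 63.8%, a mean of about 58%.

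**6. Illustration.** Day 0 is 10 March 2021; later doses are 31 March, 21 April and 12 May. Each reaction starts on the dosing day, with the day missing.

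| True onset | Imputed onset | Filed under |
|---|---|---|
| 31 March (dose 2) | 10 March | Dose 1, day 0 |
| 21 April (dose 3) | 1 April | Dose 2, day 1 |
| 12 May (dose 4) | 1 May | Dose 3, day 10, outside 7 days |

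If the protocol's anchor is read as whichever dose fits, the April and May events go to the right dose. The March event remains ambiguous, because two doses fall in March.

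**7. Would assigning the latest fitting dose be better?** Spread day-missing onsets evenly over 0-20 days after each of the four doses (730 Day 0 dates) and cap the assigned dose at the stop date where there is one. For ongoing events this finds the right dose in 52%, the same as the SAP rule, and files the other 48% too late. For 7-day events it does better (81% against 52%). But of events with true onset after day 7 it places 82% (3-day events), 89% (7-day) or 94% (ongoing) in a 7-day table, against 46% under the SAP rule.

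**The case against.** The strongest reply is about scope. SAP 3.10 limits itself to treatment emergence, and for true post-dose reactions it answers that question correctly: in the check, no reaction 0-6 days after any dose lost TEAE status. Neither document says that the imputed date also assigns the dose or the 7-day window. This stands. A reader might infer that reactions after doses 2-4 will be filed under earlier doses. The documents support only the conditional statement, together with the fact that the tables have no partial-date rule of their own.

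A reader might also infer that the missing stop-date check causes the by-dose shift. It does not; step 4 shows the shift unchanged when the check is added.

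Nor do the documents support the inference that worsening with repeat dosing would be hidden. Each subject counts once per incidence, so a moved event may change no cell. No hypothesis is tested, and every AE is listed by subject. SAP 4.4.2 names no duration table, so the negative durations have no named summary output.

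Incomplete dates may be few. Protocol 6.9 has staff assess the injection site before dosing, at least 30 minutes after it, and at the next visit, and 6.8 has AEs queried at each visit. This limits the size but does not remove the defect. The 75.3% also depends on events clustering near surgery; spread over the full 60 days it is 24.5%.

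None of this answers the first problem. The stated purpose of conservatism does not justify overriding a recorded stop date before the first dose.

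**Conclusion.** The concern holds in two parts of unequal strength.

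**Firm:** followed literally, SAP 3.10 makes some events that ended before Day 0 treatment-emergent, with impossible dates, in the primary safety analysis. With the day missing, 75.3% of events starting 1-14 days pre-dose are converted, or 24.5% over 1-60 days; a stop-date bound leaves 14.6% and 3.4%.

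**Conditional:** if the imputed date feeds the by-dose and 7-day tables, about 87% of day-missing reactions 0-6 days after doses 2-4 move to an earlier dose, and about 55% leave every 7-day table. If it does not, those tables lack a rule. Either way the SAP needs text.

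All percentages are per AE with an incomplete onset date and rest on uniform dates, nominal dose spacing and known stop dates. The documents do not give the share of such AEs. If it were 2% to 10% (an assumption), misfiled events would be 0.868 x 2% = 1.7% to 0.868 x 10% = 8.7% of dose 2-4 reactions. Overall any-TEAE incidence for true post-dose reactions does not change. This is a correction worth making before the tables are run; it does not overturn the safety analysis.

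**What to change.** 1. Add to SAP 3.10 that an AE with a known stop date before the first dose is not treatment-emergent, and that an imputed onset may never be later than the known stop date.
2. Reconcile the anchor in protocol 8.5.1 (date of treatment) with that in SAP 3.10 (start of treatment), and state which tables the imputed date feeds.
3. In the by-dose and 7-day tables, show AEs whose dose cannot be determined from the known date parts and stop date in a separate row, *dose not determinable*.
4. Use latest-fitting-dose assignment only as a sensitivity table. It should not replace the main rule, because it moves late-onset events into the 7-day window.

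The cost is a few sentences, a few lines of programming and a small extra row. No new data are needed, and the conservative intent is kept for events that may have been present on or after Day 0.
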